2. SUMMARY

Short Title	Colorectal cancer breath analysis (COBRA)
Methodology	Cohort Observational & Laboratory study
Research Site	St Mary's Hospital Charing Cross Hospital St Mark's Hospital St George's Hospital Homerton University Hospital Chelsea and Westminster Hospital West Middlesex Hospital Royal Marsden Hospital
Aims	Determine the diagnostic accuracy of the exhaled breath and urine test for the prediction of colorectal disease. To assess the acceptability of using breath and urine testing
Main Inclusion Criteria	Any patient who: 
 1. Patients aged 18 - 90 years 2. Patients seen in secondary care with symptoms of colorectal disease or referred for a lower gastrointestinal endoscopy as part of their routine clinical investigation programme 3. Patients able to understand and retain the information provided, thereby being able to give informed consent for inclusion in this study
Number of Participants	Target 2000
Endpoints	Primary endpoint 
 Once samples have been collected from 2000 patients.
Study Duration	April 2017 to April 2022

3. INTRODUCTION

3.1 Background

Colorectal cancer (CRC) is the 2nd commonest cause of cancer death in the UK. Survival rates are among the lowest in Europe (1) and 26% of patients present as an emergency, frequently having visited their GP before diagnosis (2-4). If diagnosed early, CRC survival rates exceed 90% (5). Whilst, reducing delay in diagnosis is therefore considered key to improving outcomes [6], initiatives to reduce delay have thus far been largely unsuccessful (6, 7). In order to improve the diagnosis of CRC, efforts should be made to determine how the risk of CRC can be assessed using sensitive primary care tests that are: valid; easy to perform, and; well tolerated by patients.

CRC screening programmes rely on detection of early-stage cancer using the faecal occult blood test (FOBT) with colonoscopy in those patients with a positive test. Trials have shown that this screening method reduced CRC mortality but not incidence rates. Even if UK CRC incidence rates remain constant, as they have for the past 30 years, with an aging population the number of cases and treatment cost are set to double in the next 50 years. The Bowel Scope programme is also being rolled out across the UK currently, aiming to perform flexible sigmoidoscopy on every person at the age of 55. Invasive screening reduces mortality but is not without risk to patients and pressurises an already overburdened healthcare service.

Risk of CRC in symptomatic patients can be assessed by different methods:

- (I) *Flexible sigmoidoscopy and colonoscopy*: The NHS currently has insufficient trained endoscopists to perform the number of procedures that would be required if flexible sigmoidoscopy were used as a first-line test for symptoms with predictive values below 3%.
- (II) *Guaiac FOBT* has good sensitivity (87-98% in CRC detection), but highly variable and often unsatisfactory specificity (13-79%), requiring the repetition of the test on multiple stool samples. To date, the FOBT is neither recommended nor available for use as an intermediate test (8-11).
- (III) *Faecal immunochemical testing (FIT)* requires sampling only a single stool. It has been extensively tested; and is now used by many CRC screening programmes with very low prevalence rates of CRC (12). Four FIT systems are fully automated, and provide a quantitative measure of haemoglobin, allowing selection of a threshold of positivity to fit specific circumstances. As a result the research data available on sensitivity and specificity for CRC is based on small numbers of cancers. The few studies that have included adequate numbers of cancers have used older qualitative tests with a fixed threshold for positivity and were not automated. Nevertheless, the data suggest that, depending on the selected threshold for positivity, sensitivity for CRC varies between 35% and 86% with specificity between 85% and 95% (8, 9). However, there are no data on the sensitivity of the newer quantitative test for early-stage cancers.
- (IV) *Multi-target stool DNA testing*: When compared with the FIT, in a large multicentre study, the test showed better specificity (92 vs. 73%), but lower sensitivity (90 vs. 96%) (13).

At Imperial College London, we have developed a breath test for the detection of oesophagogastric adenocarcinoma from biomarker discovery to clinical trials. The assessment of volatile organic compound (VOCs) within exhaled by selected ion flow tube mass spectrometry (SIFT-MS) (14) was followed by the construction and validation of a diagnostic model using a panel of 9 VOCs in 225 patients with an area under the ROC curve (\pm SE) of 0.92 ± 0.01 and 0.87 ± 0.03 for the model and validation subsets respectively (15). We also performed cross-platform chemical validation using GC-MS. A NIHR-funded multicentre blind validation study on 396 patients (16) showed a sensitivity of 86% and specificity of

80%. In parallel with this work we have also investigated the exhalation kinetics and molecular drivers of VOCs in oesophagogastric adenocarcinoma (17-19).

In colorectal cancer we performed a prospective pilot study to identify discriminative VOCs (n=150); a diagnostic validation study (n=110); a clinical prognostic study following surgery and after tumour recurrence (n=60); cross platform chemical validation using GC-MS (n=30). The diagnostic model had a sensitivity of 85% and specificity of 84% for cancer diagnosis. Following surgery the biomarker normalised to control level, but levels significantly increased with recurrence (20). The volatile biomarkers for oesophago-gastric and colorectal cancers are different with no overlap.

Volatile Organic Compounds (VOCs)

VOCs emitted from the human body have been of interest to researchers for several decades. In 1971, Pauling et al (21), reported that breath and urine contained approximately 250 and 280 VOCs respectively in normal human subjects. VOCs are traditionally measured in food industry and counter-terrorism (22-24).

The analysis of exhaled breath for the non-invasive detection and monitoring of disease is an attractive and evolving field of clinical research. Routine clinical applications of breath testing include the alcohol breathalyser, ¹³C urea breath test for *H. pylori*, nitric oxide in asthma, and hydrogen/methane test for bacteria overgrowth (25-29).

Alteration in VOC production in patients with cancer has been postulated to relate to oxygenation of cell membrane-based polyunsaturated fatty acids resulting from genetic and/or protein mutations within tumour cells and the increased relative prevalence of reactive oxygen species (30, 31). These VOCs produced from the cancer site within the body, travel within blood to reach pulmonary alveoli where they are exhaled, permitting an objective quantitative measurement (32). There have been early reports using VOCs to detect lung, breast, bladder, prostate and gastric cancers (33, 34). Reports on colorectal cancer had small patient cohorts and lacked validation (32, 35, 36).

Due to the complex composition of human breath a number of sophisticated mass spectrometer based technologies have been employed for the detection of exhaled VOCs including Gas Chromatography coupled with Mass Spectrometry (GC/MS), Proton Transfer Reaction-Mass Spectrometry (PTR-MS), Selected Ion Flow Tube-Mass Spectrometry (SIFT-MS) and Ion Mobility Spectrometry (IMS). These instrumental methods all have their strengths and limitations for applications in breath analysis. We intend to use multiple analytical platforms in our proposed work as these techniques are complementary and will allow us to acquire more robust findings.

Thermal-desorption (TD) coupled to Gas Chromatography Mass Spectrometry (GC/MS) is a widely adopted method for measuring breath VOCs. Although this method requires the pre-concentration of breath volatiles prior to analysis, it allows for the comprehensive identification and semi-quantification of VOCs in unknown complex mixtures such as breath. It can separate and detect hundreds of compounds from a breath sample, allowing for VOC profiling and has therefore been used in the study of disease biomarkers for lung cancer (34, 37), breast cancer (33), colorectal cancer (32) and liver diseases (38, 39).

Selective Ion Flow Tube Mass Spectrometry (SIFT-MS) permits online, real-time VOC

quantification (40). SIFT-MS has been utilised in the study of VOCs in breath and urine from patients with conditions including cystic fibrosis and bladder cancer (41, 42). The SIFT-MS technique allows real-time detection and quantification of VOCs within biological samples such as exhaled breath without any sample preparation minimising diagnostic delay.

Proton-Transfer-Reaction Time-of-Flight Mass Spectrometry (PTR-ToF-MS) is a relatively new instrumental tool that is gaining interest in breath research applications. Similarly to SIFT-MS, Proton-Transfer-Reaction Mass Spectrometry (PTR-MS) is a direct injection-based technology, obviating problems related to pre-concentration and separation steps typical of GC-MS. The most important advantage guaranteed by the ToF mass analyzer over quadrupole-based instruments (GC-MS and SIFT-MS) is represented by the high time resolution. In a ToF analyser a complete mass spectrum is generated at each ionisation event and spectra can be recorded at a frequency of 1 Hz or lower. This improves the accuracy of measurement during *in vivo* studies; moreover, full spectral scans can be performed without compromising sensitivity, thus enabling simultaneous targeted and untargeted analysis.

The use of multi-platform analytical methods will enable both compound identification and quantification which are very important in the search and validation of biomarkers.

3.2 Rationale

Colonoscopy remains the gold-standard investigation for the assessment of patients with lower gastrointestinal symptoms and considered at risk of colorectal cancer. Colonoscopy is an expensive investigation that is uncomfortable for the patient and not without important risks including visceral perforation and bleeding.

A breath test is a non-invasive investigation. The use of a breath test as a triage investigation in symptomatic patients could identify high-risk patients who should be referred for colonoscopy at an earlier stage, increase the proportion of appropriate referrals from primary care, and improve NICE guidelines which may currently miss particularly younger patients (43). If a GP is presented with a patient with gastrointestinal symptoms that do not prompt referral under NICE guidelines, he/she would not need to watch-and-wait to see if symptoms worsen but could offer the test immediately. The GP would order a breath test in much the same way as routine blood tests, with a single breath collection assessing for individual or multiple cancers. A nurse can perform the test and send breath samples to a regional laboratory for analysis. A positive result would warrant immediate referral. A negative test would permit the GP to reassure the patient and offer retesting if symptoms persist. Furthermore if we could develop a breath test that can discriminate colonic adenomas, the test would have further a potential application within the screening programme.

A breath test could also be used to detect recurrence in patients post-resection for their colorectal cancer, allowing earlier detection and limiting invasive testing in those who are free of recurrence.

Previous pilot study data for colorectal cancer detection by our group produced a diagnostic model with a sensitivity of 85% and specificity of 84% for colorectal cancer. The next stage of this research and the subject of this current proposal is to assess the influence of lower gastrointestinal diseases on VOC exhaled breath and urine. The external validation of this VOC breath model in a large multi-centre study will provide this risk-stratification tool for future clinical practice.

4. STUDY AIMS

4.1 Aims

The primary aim of this study is to determine the diagnostic accuracy of the exhaled breath and urine test for the prediction of colorectal disease.

Secondary aims are:

- (i) Refine the current diagnostic model using technologies that allow identification of additional biomarkers at a lower detection level for CRC.
- (ii) Confirm the diagnostic accuracy of the test in a new and independent group of patients who have CRC compared to subjects with benign diseases or normal colon.
- (iii) Confirm the prognostic accuracy of the test in detecting tumour recurrence after surgical removal of CRC.
- (iv) Profile VOCs in patients with colonic adenomas and construct a diagnostic model.
- (v) Profile VOCs from colonic air in a subset of patients, for use as a comparison against breath testing in order to improve understanding of underlying pathological mechanisms.
- (vi) To assess the acceptability of using breath and urine testing

5. METHODOLOGY

5.1 Inclusion Criteria

Any patient who is:

- ≥ 18 years old and below 90 years of age, AND:
- undergoing a lower gastrointestinal endoscopy as part of their routine clinical care OR:
- seen in another hospital clinical setting with symptoms of lower gastrointestinal disease
- able to provide informed written consent

5.2 Exclusion Criteria

Any patient who:

- Lacks capacity or is unable to provide informed consent.
- Any patient below 18 years of age or over 90 years of age.

5.3 Study Design and Plan

Patients recruited from the endoscopy unit will have been referred by their responsible clinician to undergo a lower gastrointestinal endoscopy (which involves a telescope test to visualise the colon). Others may be attending for colonoscopy as part of the bowel cancer screening programme or as part of routine surveillance. When patients attend the endoscopy unit, a member of the research team will discuss the research project with the patient, explain that the study involves sampling of their breath and urine while they are waiting for their endoscopy. Patients may also be asked to consent to the use of the colonic air collected during colonoscopy for analysis. Patients will then be provided with a patient

information leaflet, (see Participant Information Leaflet version 3.0 24/04/2017). Should the patient agree to participate they will be asked to sign a written consent form (see Consent Form Version 2.0 15/02/2017).

Patients recruited from secondary care will be approached either before or after a routine appointment that they will be attending as part of their clinical care. This could include general colorectal clinics, pre-operative colorectal clinics, oncology clinics, theatres or on hospital wards.

The project will be explained to them and they will be provided with an information leaflet. If they agree to participate they will be asked to sign a written consent form in order to provide breath and urine samples for the research project. Consent for colonic air sampling is not applicable to the majority of secondary care patients, only to those having a colonoscopy. No additional invasive procedures will be undertaken for the purposes of this study. A subset of patients with known cancer who are due to have a cancer resection may be asked to provide additional breath and urine samples 6–8 weeks following surgical resection of their tumour and/or if their disease should recur.

Patients attending for colonoscopy will be fasted for a minimum of six hours prior to their breath sample collection. This is normal routine practice for patients undergoing endoscopy and therefore will not alter their treatment pathway. All breath samples will be retrieved prior to endoscopy. In other secondary care settings patients will not be specifically asked to fast prior to giving breath or urine samples but note will be made of how long they have fasted for. Patients will be asked to give a number of exhalations into a breath sampling device until a defined volume of breath has been sampled. This involves performing normal tidal breathing whilst wearing a face mask, and takes around 2 minutes on average. Patients will also be asked to perform a single deep nasal inhalation followed by complete exhalation via their mouth into a secure GastroCHECK steel breath bag (500 mL) via a 1 mL Luer-Lok syringe (Terumo Europe, Leuven, Belgium). Patients at St Mary's Hospital will also be asked to breathe directly into a mass spectrometer machine. The mass spectrometer is a self-contained mobile device which can be easily moved between clinical areas within St Mary's Hospital. Sampling by this method will involve a single deep nasal inhalation followed by complete exhalation via their mouth into a plastic cylinder connected to a tube leading to the mass spectrometer itself. We expect the breath sampling process to take no longer than 5–10 minutes in total. Patients will be requested to pass urine into a standardised 60ml urine specimen vial, which will be immediately sealed. 20ml of urine will be aliquoted into a standard 60ml specimen vial.

Of patients attending for colonoscopy, a subset will be asked to consent to have air from their colon collected. This air comes up from the colon through the colonoscope suction channels. Suctioning of air is a routine part of the examination, but for this study we will be collecting it for analysis. Collection is done via a small suction pump connected to a fine bore tube that is passed through the suction channel of the colonoscope. Sampling in this way will add no more than a few minutes (<4 minutes) on to the procedure time.

The VOCs from the breath/colonic air will be trapped onto adsorbent tubes inserted into the breath taking device. In the case of colonic air sampling, an adsorbent tube is attached to the pump end of the fine bore disposable suction tube. After sampling the adsorbent tube is removed from the device, capped and transported back to the laboratory at St Mary's Hospital London for analysis. Samples will be transported by courier or by a member of the research team. The sample(s) shall undergo analysis via our mass spectrometry instruments, at St Mary's Hospital London.

Breath samples collected in steel bags will be immediately disposed of following analysis within 6 hours of the sample being taken. Breath VOCs sampled on adsorbent tubes will be

analysed within 48 hours of collection. The sample constituents are destroyed within the mass spectrometer for detection meaning that no clinical material will remain after analysis by GC-MS. Urine samples will be stored within a registered tissue bank (REC Ref no. 04/Q0403/119, custodian Prof [name]) in accordance with the Human Tissue Act and disposed of following analysis.

This study has been specifically designed to ensure that any disruption to patient's routine care and management is kept to an absolute minimum.

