7. STATISTICAL CONSIDERATIONS

Both univariate and multivariate data analysis techniques will be applied to the results to 1) identify VOC components with the best discriminating ability between the groups and 2) to develop a multivariate discriminant analysis model.

Mann-Whitney U test will be used to compare the measured metabolite concentrations between the study groups. A p value <0.05 will be taken as the level to indicate statistical significance.

Non-parametric (Kruskal-Wallis) ANOVA test will be used to compare the measured metabolite levels between the study groups. Statistically significant metabolites will be selected using False Discovery Rate (FDR) adjusted p value threshold such that less than 5% of discovered candidate markers are false positives (i.e. q-value <0.05).

The FDR strategy will be based on Benjamini-Hochberg procedure.

Receiver operating characteristic (ROC) curves will be used to determine the accuracy of a diagnostic test in classifying those with and without colorectal disease. The metabolite concentrations that exhibit significant differences ($q < 0.05$) between the cancer and positive controls (including adenomatous polyps) will be included as variables for the proposed diagnostic test. The linear discriminant analysis based on multivariate logistic regression will be subsequently used to derive a combination of the metabolite concentrations for sample classification. The optimum threshold for group discrimination will be calculated to achieve the highest possible classification accuracy. The predictive capacity of the model will be assessed on independent sample set, as described below.

Validation

The Breath and Urine metabolite model for the prediction of colorectal disease developed in the previous studies will be used to assign risk of disease in a prospective cohort. Investigators undertaking metabolite sampling and analysis will be blinded to the results of the endoscopy. Comparison of predicted disease risk and actual endoscopy findings will then be made, and the overall diagnostic accuracy (sensitivity, specificity, positive and negative predictive value, ROC curve analysis) for this non-invasive diagnostic investigation will be determined. Colonic air VOC profiles will be used for validation of paired breath results, and to gain further understanding of the mechanism of VOC production in humans.

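### Aim (iii) promises accuracy for detecting recurrence, but the designated post-operative samples confound recurrence with time since surgery and no late recurrence-free comparator is named

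*Combined protocol and SAP*

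**What the plan says.** Section 4.1 of the combined protocol and SAP words aim (iii) as a confirmatory accuracy aim: "Confirm the prognostic accuracy of the test in detecting tumour recurrence after surgical removal of CRC".

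Section 5.3 describes the sampling that serves it. "A subset of patients with known cancer who are due to have a cancer resection may be asked to provide additional breath and urine samples", and the times are "6–8 weeks following surgical resection of their tumour and/or if their disease should recur". No subset size, serial schedule or length of follow-up per patient is given.

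Section 7 contains no analysis specific to aim (iii):

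- For two groups: "Mann-Whitney U test will be used to compare the measured metabolite concentrations between the study groups".
- For several groups: "Non-parametric (Kruskal-Wallis) ANOVA test will be used to compare the measured metabolite levels between the study groups".
- For validation, the reference is endoscopy: "Comparison of predicted disease risk and actual endoscopy findings will then be made". No reference standard for recurrence is stated.
- Pairing is mentioned once, for a different purpose: "Colonic air VOC profiles will be used for validation of paired breath results".

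**The concern.** The late post-operative sample is triggered by the outcome that the test is meant to detect. A patient who stays free of recurrence has no designated sample after week 8. A patient who recurs gives one later, once the recurrence is known. Anything that changes a breath or urine profile between those two times, such as later treatment, will look like a recurrence signal.

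Section 3.2 shows what is at stake. It foresees using the test after resection to find recurrence earlier and to spare recurrence-free patients invasive tests. That use depends on specificity in recurrence-free patients at surveillance times, for which the plan designates no data. Section 3.1 reports that the marker normalised after surgery and rose at recurrence. A time effect in the same direction would appear to confirm that pattern.

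A lesser matter is that before-resection, 6–8 week and recurrence samples come from the same people, while the only group tests named are for independent groups.

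**Working it through.** The plan states no sample size, effect size or event count for aim (iii), so it has no figure to reproduce. The check has three steps. The first needs only the text; the other two are illustrations on assumed values.

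**1. Which samples exist under Section 5.3**

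| | 6–8 weeks | Later |
|---|---|---|
| Recurrence-free | designated | none designated |
| Recurrence | not applicable at this visit, unless recurrence is very early | designated |

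Recurrence-free samples all lie at one time and recurrence samples at other times. Recurrence and time since surgery are aliased, and no numerical assumption is needed to see it.

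**2. Apparent accuracy from a time shift alone**

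Assume normal marker values with equal variance, no recurrence effect, and a shift of d SD between 6–8 weeks and the later sample. Then AUC = Φ(d/√2).

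- d = 0.3: Φ(0.212) = 0.58
- d = 0.5: Φ(0.354) = 0.64
- d = 0.75: Φ(0.530) = 0.70
- d = 1.0: Φ(0.707) = 0.76

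With no information the AUC is 0.5. The documents give no basis for any particular d.

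**3. Paired data and the named tests**

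If an independent-group test were applied to n pre/post pairs with within-patient correlation ρ, its true two-sided size at a nominal 0.05 would be about 2·[1 − Φ(1.96/√(1 − ρ))]. This gives 0.019 at ρ = 0.3, 0.006 at ρ = 0.5 and 0.0003 at ρ = 0.7. The test is conservative, so the loss is in power. Simulation (3000 runs per cell, bivariate normal pairs, true change 0.5 SD) gives:

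| Pairs | ρ | Mann-Whitney power | Signed-rank power |
|---|---|---|---|
| 20 | 0.5 | 26% | 52% |
| 30 | 0.5 | 44% | 73% |
| 40 | 0.3 | 58% | 72% |
| 40 | 0.5 | 60% | 85% |
| 40 | 0.7 | 63% | 97% |

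Number of pairs, ρ and the 0.5 SD change are all assumed.

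A paired test does not cure the problem in step 2. With no recurrence effect, a time drift of 0.5 SD and ρ = 0.5, the signed-rank test still rejects in 53% of runs with 20 pairs and 86% with 40. These are its power figures again, within simulation error, because the test sees the same data whether the change comes from recurrence or from time.

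**The case against.** Several stronger readings are tempting, and the documents do not support them.

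*That the study cannot estimate accuracy for recurrence at all.* Section 5.3 allows recruitment at routine surveillance colonoscopy and in oncology clinics, so late recurrence-free patients may be among those sampled. The comparator is undesignated rather than impossible. The opposite assumption, that suitable comparators are already in hand, is not shown either. Section 5.3 does not say that surveillance is post-resection, Section 5.1 requires lower gastrointestinal symptoms of patients recruited outside endoscopy, and nothing says that date of resection is recorded.

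*That instrument drift is built into the contrast.* Section 6.1 has recruitment running from April 2017 to March 2022. One patient's recurrence sample and another's 6–8 week sample can fall in the same calendar period, which partly breaks that link. Fasting time is noted outside endoscopy (Section 5.3), which covers part of diet. Later treatment is the stronger mechanism.

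*That Section 7 treats pre/post pairs as independent groups.* It applies its tests between study groups and never says they will be used on repeated samples. For a comparison of patients with and without recurrence, each counted once, an independent-group test is valid. The gap is silence about the within-patient analysis. If the tests were misapplied, power would be lost and false positives would not increase.

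It is also fair to say that this is one of six secondary aims, in an optional subset. What stands is that the aim is worded as confirmation of accuracy, while the designated samples have no late recurrence-free group and no stated reference standard for recurrence.

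**Conclusion.** The point holds in this form: as designated, the samples for aim (iii) confound recurrence with time since surgery, and the plan names no comparator, reference standard or analysis that would separate them. This follows from Sections 4.1, 5.3 and 7 without numerical assumptions.

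The size does rest on assumptions. A shift of 0.3 to 0.5 SD unrelated to recurrence would give a spurious AUC of 0.58 to 0.64. The unpaired-test issue is secondary and conditional: about 44% against 73% power with 30 pairs, a 0.5 SD change and correlation 0.5, all assumed. The primary accuracy aim is untouched, but aim (iii) should not be reported as confirmed accuracy on these samples.

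**What to change.** **Preferred.** Restate aim (iii) as an exploratory description of within-patient change before resection, at 6–8 weeks and at recurrence. Add a sentence to Section 7 naming a paired or mixed-model analysis. A mixed model suits the and/or sampling because it accepts incomplete sets. State that this analysis does not remove confounding with time since surgery and supports no accuracy claim.

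**If an accuracy figure is kept:**

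- designate as comparators recurrence-free post-resection patients among those recruited at routine surveillance colonoscopy;
- record date of resection, and match or adjust for time since surgery;
- match or adjust for fasting, since Section 5.3 has colonoscopy patients fasted for at least six hours and others not asked to fast;
- state the reference standard for recurrence;
- count each patient once in the comparison.

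**Cost.** The preferred option changes the wording of one secondary aim and adds a sentence or two of analysis, at the price of a weaker claim. The accuracy option adds one or two recorded items, and it depends on enough suitable surveillance patients being recruited, which the documents do not establish. Neither option requires an additional invasive procedure.
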